
Overall Study Aim

The overall aim of this Phase II, proof of concept study is to evaluate the efficacy and safety of naloxegol (versus placebo) in preventing lower GI tract paralysis in critically ill adults initiated on scheduled intravenous (IV) opioid therapy.

2. 1 Primary objective

The primary objective of this single-center, Phase II, proof of concept study in critically ill adults initiated on scheduled IV opioid therapy is to compare the incidence of lower GI tract paralysis [from the time of a study enrollment (i.e., randomization) to ICU discharge, death or 10 days of study drug administration (whichever comes first)] between naloxegol 25mg daily and placebo-treated groups.

Drug Substance: Movantik
 Study Number: ESR-15-11000
 Tufts IRB #12043
 Version: Protocol version #19
 Date: September 10, 2018

Note:

1. For the purposes of the study, any rectal output will be considered a SBM as long as it is not temporally related to the insertion of a rectal tube or the insertion of a suppository (as per the study laxative protocol (Appendix 1)).
2. Patients with preexisting lower GI tract paralysis are excluded from the study.
3. Patients not expected to survive their ICU stay are excluded from the study.

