5.6 Concomitant and post-study treatment

All patients enrolled in the study will be initiated on the following:

1. Docusate 100mg twice daily administered orally (or enterally).

AND

2. Study Laxative Guideline (see Appendix 1)

Drug Substance: Movantik
Study Number: ESR-15-11000
Tufts IRB #12043
Version: Protocol version #19
Date: September 10, 2018

A standard laxative guideline does not currently exist in any ICUs at Tufts Medical Center. Therefore in an effort to standardize the administration of laxatives in the study, the investigative team developed a study laxative guideline that is similar to current laxative prescribing practices in the medical ICU at Tufts MC for patients that do not have spontaneous bowel movement for ≥ 3 days. Realizing the importance of having a formal, tiered laxative guideline that mimics that which is used in routine practice for medical ICU patients at Tufts Medical Center, the investigators basically formalized the approaches that are most commonly used in practice to develop (what is felt) to be a reasonably aggressive guideline. It should be noted that if study patient fails to have spontaneous bowel movement at 6 days (despite ever more intensive laxative treatment steps occurring), the patient will be removed from the study and the clinical ICU team will have the option of administering SC methylnaltrexone or intervening in whatever way these see fit to treat the constipation. Of course, prior to study day #6, if the medical ICU team feels that a subject's constipation is severe enough to warrant study removal (and perhaps methylnaltrexone administration) then the subject would be removed from the study earlier. It will be communicated to each subject's ICU physician that the study laxative guideline does not have to be rigidly followed if the subject's physician deems that a deviation from the guideline is required based on their clinical evaluation of the subject.

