5.8 Discontinuation of investigational product

5.8.1. Procedures for discontinuation of a subject from investigational product

Study drug administration will be stopped when one of the following occurs:

1. The subject experiences an adverse event potentially attributable to the study drug that is deemed, in the opinion of principal investigator, to warrant discontinuation of therapy.
2. The patient requires use of the Level 4 Study Laxative Guideline (i.e., methylnaltrexone)
3. Scheduled opioid therapy is stopped for ≥ 24 hours and the patient has had ≥ 1 SBM since the time of study enrollment.
4. The patient has been administered 10 days of study medication.
5. The patient is discharged from the ICU.
6. The patient dies in the ICU.
7. The patient requires a strong CYP3A4 inhibitor medication (and no other therapeutic alternative medication without this property can be used)
8. The patient develops excessive diarrhea defined as ≥ 3 SBMs with a Bliss Score of 3 or 4 in a 24 hour period. When excessive diarrhea first occurs, study medication will be held. In addition, all laxatives

Drug Substance: Movantik
 Study Number: ESR-15-11000
 Tufts IRB #12043
 Version: Protocol version #19
 Date: September 10, 2018

will be stopped (including docusate) and the investigative team will work with the subject's clinical team to identify other possible causes for the excessive diarrhea (e.g. enteral nutrition formulation choice, C. difficile infection etc). In a further 24 hours (48 hours after the last study medication dose), if excessive diarrhea persists, the study medication will be permanently discontinued. However, if the subject no longer has excessive diarrhea in a further 24 hours (48 hours after the last study medication dose), study medication will be resumed at the original dose. If excessive diarrhea occurs again after study medication is resumed, then the study medication will be permanently stopped.

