5.9 Withdrawal from study

While 5.8.1 lists the reasons why study drug administration will cease, post-study drug discontinuation outcomes like duration of ICU stay will still be collected.

Should consent for study participation be withdrawn all study data collection activities will cease and no study data collected before the time of withdrawal will be used.

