12. STATISTICAL METHODS AND SAMPLE SIZE DETERMINATION

12.1 Description of analysis sets

All patients will be analyzed in the groups to which they were randomly assigned, according to the intention-to-treat principle.

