12.2 Methods of statistical analysis

[figure not shown]
Baseline characteristics of patients will be compared using standard univariate methods (chi-square test, t-test) to confirm the randomization was successful in achieving comparable groups. To test the primary outcome (incidence of lower GI tract paralysis), given that there may be censoring (i.e., subject may die or withdraw from study before developing lower GI tract paralysis), we will present Kaplan-Meier curves for the naloxegol and placebo groups for the time to first development of lower GI tract paralysis (≥ 3 days without a SBM after study randomization) during the ICU stay up to 10 days and compare the curves using a log-rank test. If all subjects complete the study (e.g., no deaths, no withdrawal or loss-to-follow-up for other reasons), then we will instead compare the proportion of patients that develop lower GI tract paralysis after study randomization during the ICU stay up to 10 days between the naloxegol and placebo groups using a chi-square test. The secondary outcome, time to first SBM will be estimated using a Kaplan Meier time to event analysis and compared between groups using a log-rank test. The secondary outcome of the number of ICU days without a SBM will be compared between the naloxegol and placebo groups using the Poisson regression for count data and adjusting for total number of days in the ICU (up to a maximum of 10) as an offset term in the Poisson model. The secondary outcome of the average daily opioid requirements will be compared between groups using either a student t-test or nonparametric Wilcoxon rank-sum test if the assumptions of the student t-test fail to be met. Length of mechanical ventilation and ICU stay will be reported as medians and interquartile ranges and will be compared using the Wilcoxon Rank Sum Test. For all statistical tests of hypotheses, a two-sided p-value of ≤ 0.05 will be considered as statistically significant. As this is a Phase II proof of concept study a p value of <0.10 may still be worth consideration for future study, however. All statistical analyses will be performed using SPSS 17.0. (SPSS, Chicago, IL) or other comparable commercially available statistical software.

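### Does the primary analysis need a written rule for a patient removed or rescued for constipation in the first 72 hours?

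*Protocol*

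**What the plan says.** Protocol 5.6 takes a patient out at six days without a SBM and allows it sooner on the ICU team's judgement: if the "constipation is severe enough to warrant study removal (and perhaps methylnaltrexone administration) then the subject would be removed from the study earlier". It also tells physicians that the laxative guideline need not be followed rigidly.

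Section 12.2, the same in protocol and SAP, dates the primary event at "first development of lower GI tract paralysis (≥ 3 days without a SBM after study randomization) during the ICU stay up to 10 days". It chooses Kaplan-Meier curves and a log-rank test "given that there may be censoring (i.e., subject may die or withdraw from study before developing lower GI tract paralysis", and changes to a chi-square test if everyone completes.

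Other passages bear on the same patient:

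- Protocol 2.1 sets the outcome window "from the time of a study enrollment (i.e., randomization) to ICU discharge, death or 10 days of study drug administration (whichever comes first".
- Note 1 there says "any rectal output will be considered a SBM as long as it is not temporally related to the insertion of a rectal tube", and makes the same exception for suppositories.
- Protocol 5.8.1 item 2 lists, as a reason to stop study drug, "The patient requires use of the Level 4 Study Laxative Guideline (i.e., methylnaltrexone". Appendix 1 Step 4 likewise stops study medication and does not mention leaving the study.
- Protocol 5.9 says that "post-study drug discontinuation outcomes like duration of ICU stay will still be collected", and ends data collection only when consent is withdrawn.
- SAP 12.1: "All patients will be analyzed in the groups to which they were randomly assigned, according to the intention-to-treat principle".

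**The concern.** A patient taken out for severe constipation leaves because of the condition that the primary outcome measures. If this happens before 72 h, the wording allows two unwelcome results.

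- **Censoring.** If removal is a withdrawal in the sense of 12.2, the patient is censored before any event is possible, is in no log-rank risk set and can never be a failure. That censoring is informative.
- **Credit.** If only study drug stops and follow-up continues, Note 1 excepts tube- and suppository-related output but not output after methylnaltrexone. A successful rescue could then be scored as successful prevention.

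With 18 patients per arm, a few such decisions could move the result. Section 5.6 speaks of removal from the study where 5.8.1 and Appendix 1 speak only of stopping study drug, so two analysts might score the same patient differently.

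**Working it through.** **The plan's own figure.** The table in 12.2.2 gives 99.8% power for 90% vs 40% at alpha 0.05 with complete follow-up. It reproduces if time to defecation is exponential and followed for 10 days. The hazard ratio is ln(0.4)/ln(0.9) = 8.70. Expected events are 18 × [(1 − 0.9^2.5) + (1 − 0.4^2.5)] = 20.4. Schoenfeld's formula gives Φ(√(20.4/4) × ln 8.70 − 1.96) = 99.8%. That models time to defecation, so it is not the baseline for the paralysis endpoint used below.

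**Who is affected.** Appendix 1 counts from the start of scheduled opioids, so Step 4 is due at 6 × 24 = 144 h. Exclusion (o) requires enrolment and first dose within 72 h of opioid start. Counted in hours, scheduled Step 4 therefore falls at least 144 − 72 = 72 h after randomisation. A patient with no SBM since randomisation who is removed at or after 72 h has already had the event. That leaves discretionary removal in the first 72 h. Removal inside a later gap of under three days raises the same question and is not modelled.

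**Which reading the text supports.** Only the phrase in 5.6 supports treating removal as withdrawal. The window in 2.1 does not end at removal, 5.8.1 and Appendix 1 stop study drug only, 5.9 keeps collecting outcomes, and 12.1 applies intention to treat. Table 1 lists SBM charting as routine nursing care. Under continued follow-up there are two outcomes: no qualifying output means a failure at 72 h; qualifying output with no later three-day gap means no failure. Step 4 repeats the bisacodyl suppository of Step 2, so output after a guideline-style rescue may not qualify.

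**Size.** Inputs: 18 per arm and two-sided 0.05 (12.2, 12.2.2). The failure proportions 90% vs 40% and 80% vs 50% are taken from the power table. Assumed, because the documents give no figure: q, the share of would-be failures removed or rescued before 72 h, and s, the share of rescues giving qualifying output before 72 h. With p the true failure proportion, the apparent proportion is:

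- censored: p(1 − q)/(1 − pq), with removed patients out of the risk set;
- followed: p(1 − qs).

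For q = 10% and 90% vs 40%, censoring gives 0.81/0.91 = 89.0% vs 0.36/0.96 = 37.5%. Following with s = 1 gives 81% vs 36%. Expected removals are 18 × (0.9q + 0.4q): 1.2, 2.3 and 4.7 patients for q = 5%, 10% and 20%.

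Exact power of the log-rank test at a single 72 h event time:

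| Failure proportions, q | Censored | Followed, s = 0.5 | Followed, s = 1 |
|---|---|---|---|
| 90% vs 40%, none | 92.7% | 92.7% | 92.7% |
| 90% vs 40%, 5% both arms | 92.0% | 90.7% | 88.5% |
| 90% vs 40%, 10% both arms | 91.2% | 88.5% | 84.0% |
| 90% vs 40%, 20% both arms | 89.5% | 84.0% | 73.7% |
| 90% vs 40%, 30% placebo only | 77.1% | 65.8% | 32.5% |
| 90% vs 40%, 30% naloxegol only | 96.9% | 97.0% | 99.0% |
| 80% vs 50%, none | 49.8% | 49.8% | 49.8% |
| 80% vs 50%, 10% both arms | 46.2% | 45.6% | 41.8% |

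The followed columns ignore later three-day gaps up to day 10, so their losses are upper bounds.

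**Would scoring these patients as failures at 72 h be better?** It restores the power, but it treats everyone removed as a certain failure. Type I error with 80% failure in both arms, 24% of one arm only removed, and a fraction f of those removed who would have had a SBM by 72 h:

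| f | Censored | Failure at 72 h |
|---|---|---|
| 0 | 7.2% | 4.8% |
| 25% | 4.6% | 7.2% |
| 50% | 8.1% | 16.3% |

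With 24% removed in both arms, both rules stay at or below 5%. With 8% of one arm removed, all values lie between 4.8% and 5.8%.

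**The case for a change.** The best argument for acting is that a scoring sentence costs little and is best fixed before unblinding. Some of it stands. Section 12.2 is silent, 5.6 does not match 5.8.1 and Appendix 1, and 5.9 gives only ICU stay as its example. Early removal is also plausible. With a 48 h lag from opioid start to enrolment, guideline Steps 1 and 2 fall due 24 h and 48 h after randomisation, so a patient may already look resistant to laxatives by then.

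The reading the documents favour is also the one with the larger possible loss. If 24% of one arm only were removed, none of whom would have had a SBM, and every rescue produced credited stool, type I error would reach 34.7%. That needs removal to differ sharply between arms with equal failure proportions. The ICU team is blinded (5.4.1), and nothing in the documents suggests such a difference.

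The log-rank or chi-square switch in 12.2 might turn on whether removal is a withdrawal. At a single event time this matters little, because the log-rank statistic is Pearson's chi-square times (N − 1)/N, here 35/36.

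The remedy is also selective. Note 1 counts stool after senna, polyethylene glycol and magnesium citrate as a SBM, and those guideline steps can fall before 72 h. Disqualifying only methylnaltrexone output would treat one rescue differently without a stated reason. Counting removal as failure would make a bedside judgement part of the endpoint.

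**Conclusion.** No change follows. This is a gap that an analyst can fill from the plan's own text: keep following the patient to the end of the window in 2.1, apply the SBM definition as written, and analyse by assigned group. A patient with no qualifying output is then a failure at 72 h without any new rule. The mismatch between 5.6 and 5.8.1, 5.9 and Appendix 1 is one of wording. Those passages should agree with one another, but the analysis does not depend on it.

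Under equal removal of 5% to 10% of would-be failures, the cost at 90% vs 40% is 0.7 to 1.5 points of power if they are censored (92.7% to 92.0% or 91.2%). If every rescue is credited, it is at most 4.2 to 8.7 points (to 88.5% or 84.0%). Larger losses need more removals, or removal concentrated on placebo. The failure-at-72-h rule is a choice of estimand that does better in some cases and worse in others.

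The conclusion rests on assumed removal shares, on a blinded team removing similar shares of would-be failures in both arms, and on SBM charting continuing after study drug stops. If many patients were in fact removed within 72 h, mostly in one arm, the choice of scoring would matter.

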5.7 Treatment compliance

Given that study drug administration will only occur in an ICU, and all drug will be administered by an experienced ICU nurse, treatment compliance should not be an issue. The usual medication administration and documentation system will be employed for the study that involves the bedside nurse bar-scanning each study drug dose (to ensure correct patient and correct schedule) and the exact time each daily study drug dose is administered will be documented. The investigative team will be in the ICU each morning to monitor all study procedures completed over the past 24 hours and will be available by pager on a 24/7 basis for any questions that the bedside nurse or any other member of the ICU clinical team may have regarding the study. The study procedures outlined in Table 1 that will be completed by a member of the investigative team will be completed by [name], [name], [name] or [name].

5.8 Discontinuation of investigational product

5.8.1. Procedures for discontinuation of a subject from investigational product

Study drug administration will be stopped when one of the following occurs:

1. The subject experiences an adverse event potentially attributable to the study drug that is deemed, in the opinion of principal investigator, to warrant discontinuation of therapy.
2. The patient requires use of the Level 4 Study Laxative Guideline (i.e., methylnaltrexone)
3. Scheduled opioid therapy is stopped for ≥ 24 hours and the patient has had ≥ 1 SBM since the time of study enrollment.
4. The patient has been administered 10 days of study medication.
5. The patient is discharged from the ICU.
6. The patient dies in the ICU.
7. The patient requires a strong CYP3A4 inhibitor medication (and no other therapeutic alternative medication without this property can be used)
8. The patient develops excessive diarrhea defined as ≥ 3 SBMs with a Bliss Score of 3 or 4 in a 24 hour period. When excessive diarrhea first occurs, study medication will be held. In addition, all laxatives

Drug Substance: Movantik
 Study Number: ESR-15-11000
 Tufts IRB #12043
 Version: Protocol version #19
 Date: September 10, 2018

will be stopped (including docusate) and the investigative team will work with the subject's clinical team to identify other possible causes for the excessive diarrhea (e.g. enteral nutrition formulation choice, C. difficile infection etc). In a further 24 hours (48 hours after the last study medication dose), if excessive diarrhea persists, the study medication will be permanently discontinued. However, if the subject no longer has excessive diarrhea in a further 24 hours (48 hours after the last study medication dose), study medication will be resumed at the original dose. If excessive diarrhea occurs again after study medication is resumed, then the study medication will be permanently stopped.

Non-study naloxegol is currently not available at Tufts Medical Center given that it has not been added to the Tufts Medical Center medication formulary so there is no chance that a patient will be initiated on naloxegol after removal from the study while still a patient at Tufts Medical Center. The care team for all patients removed from the study (who may have been receiving naloxegol) will be notified that they should formally evaluate the patient for appropriate laxative orders, particularly in those situations where opioid therapy is continuing or where the patient has not had recently had spontaneous bowel movement.

5.9 Withdrawal from study

While 5.8.1 lists the reasons why study drug administration will cease, post-study drug discontinuation outcomes like duration of ICU stay will still be collected.

Should consent for study participation be withdrawn all study data collection activities will cease and no study data collected before the time of withdrawal will be used.

6. COLLECTION OF STUDY VARIABLES

6. 1 Recording of data

As outlined above in Table 1, study data that is not routinely documented on the ICU flowsheet or within the other section of the patient record (e.g. Soarian) will be documented by the bedside nurse on a daily nursing bedside data collection form (Appendix 9). All other study data will be collected by the investigative team (Drs. [name], [name], [name] or [name]) on the daily investigative team data collection form (Appendix 10).

6.3 Efficacy

6.3.1 List each efficacy variable

As outlined in Table 1:

Any SBMs

Characterization of each SBM for size (small, medium or large)

Characterization of each SBM for consistency (using the Bliss Stool Scale)

Use of the study laxative guideline

Daily volume of enteral nutrition administered

Daily enteral nutrition goal

Daily fluid balance (i.e., 24 hr ins and outs)

Drug Substance: Movantik
 Study Number: ESR-15-11000
 Tufts IRB #12043
 Version: Protocol version #19
 Date: September 10, 2018

Pain scale score (using nurse-administered 10 point rating scale) every 6 hours
 Opioid requirement [in IV fentanyl equivalents (mcg)](all IV, SC, oral or transdermal use)
 Daily Sedation Assessment Scale (SAS) score (by nurse every q6h)
 Delirium using the Intensive Care Delirium Screening Checklist (ICDSC) (by nurse q12h)
 Daily total sedation administered (in midazolam equivalents)
 Occurrence of lower GI tract paralysis requiring consultation by a gastroenterologist or a surgeon
 Requirement for mechanical ventilation support
 Abdominal pressure (estimated by nurse measurement of bladder pressure every 8 hours

6.4 Safety

6.4.1 List of each safety variable

As outlined in Table 1:

Presence of diarrhea
 Presence of diaper
 Presence of rectal tube
 Difference in the pre-dose and post-dose Clinical Opioid Withdrawal Scale (COWS) score (as evaluated by the bedside nurse before and 2 hours after the administration of the daily study drug dose).

6.4.2 Definition for a serious adverse events and unanticipated problems:

Serious Adverse Event:

Events of a serious nature even if not related to the study (e.g. resulted in death, was life-threatening, resulted in hospitalization or prolongation of existing hospitalization, resulted in persistent or significant disability/incapacitation, may jeopardize the subject's health and may require medical or surgical intervention to prevent one of the other outcomes listed above).

Unanticipated Problem:

An event that meets all of the following criteria: 1) was unexpected; 2) was related or probably related to participation in the study, 3) may place subject(s) or others at greater risk of harm than previously recognized.

Please note that these can include:

- i. events that are identified in the ICF, but that are more severe and longer lasting than expected.
- iii events that were not expected to occur during the course of the study and that are not identified in the ICF(s).
- iv. any event about which the Principal Investigator is unsure, whether or not it meets the above criteria

